5.5.2.3. Efficacy Analyses for Long Term Extension

Efficacy in the LTE period (from Week 52 through the end of the study) will be summarized for all subjects who entered LTE.

- The proportion of PASI responses (PASI 50, 75, 90, and 100) will be summarized over time through the end of the study.
- The proportions of subjects achieving an IGA score of cleared (0); an IGA score of cleared (0) or minimal (1); and an IGA score of mild or better (≤ 2) will be summarized over time through the end of the study.
- The percent improvement from baseline in PASI will be summarized over time through the end of the study.
- BSA involved and change from baseline in BSA will be summarized over time through the end of the study.

In addition, PASI responses, IGA responses, percent improvement in PASI, and change in BSA will be summarized at Week 60 and Week 84 after retreatment among guselkumab subjects who were withdrawn from guselkumab at Week 16 and were subsequently retreated upon loss of response or at Week 52 if a loss of response was not observed at or prior to Week 52.

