### 2.1. Study Rationale

This study will evaluate the efficacy and safety of guselkumab for the treatment of chronic plaque psoriasis in pediatric participants aged  $\geq 6$  through  $< 18$  years using a placebo control and an active comparator (ENBREL® [etanercept]) through Week 16 by means of:

- comparison of guselkumab to placebo to establish the efficacy of guselkumab.
- utilization of etanercept as a benchmark for efficacy.
- collection of safety and tolerability data for guselkumab in the pediatric plaque psoriasis population.

This study will also provide an evaluation of safety and the ability to recapture response with retreatment following withdrawal from guselkumab.

In addition, the pharmacokinetics (PK) of guselkumab will be evaluated in this study to determine whether the proposed weight-based dose in children with plaque psoriasis achieves PK exposure comparable to that established in adults with the approved dose regimen. Furthermore, evaluations will be done to assess whether, with comparable exposure, the observed clinical response in pediatric participants treated with guselkumab is consistent with that observed in adults.

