**Long-term Extension (From Week 52 until study termination)**

Following completion of the Week 52 visit, participants who have had a beneficial response from guselkumab treatment as determined by the investigator, and are willing to continue guselkumab treatment, may enter the LTE of the study. Participants who decide to participate in the LTE will continue to receive guselkumab at Week 52 and q8w thereafter until one of the following occurs:

- The participant turns 18 years of age and resides in a country where marketing authorization has been granted for guselkumab treatment of plaque psoriasis in adult patients, and have had the opportunity to complete up to 1 year in the LTE.
- Marketing authorization is obtained for guselkumab for treatment of plaque psoriasis for patients  $\geq 6$  to  $< 18$  years of age in the participant's country of residence.
- Marketing authorization is denied for guselkumab for the treatment of plaque psoriasis for patients  $\geq 6$  to  $< 18$  years of age in the participant's country of residence.
- A company decision is made to no longer pursue an indication in plaque psoriasis in the pediatric population ( $\geq 6$  to  $< 18$  years of age) in the participant's country of residence.

Participants in Part 1 who continue in the LTE portion of the study will receive guselkumab as follows:

- Participants withdrawn from guselkumab or placebo at Week 16 who meet loss of response criteria and are retreated with or initiated guselkumab prior to Week 52 and receive guselkumab at Week 48 will not receive study intervention administration at Week 52 and will resume guselkumab administration at Week 60 and q8w thereafter.
- Participants who meet loss of response criteria at Week 48 will receive guselkumab at Weeks 48 and 52 followed by q8w administration beginning at Week 60.
- Participants withdrawn from treatment at Week 16 who have not been retreated with guselkumab prior to Week 52 will receive a weight-based guselkumab dose at Week 52 and q8w thereafter.

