5.1.2.2. Psoriasis Area and Severity Index

The PASI is a system used for assessing and grading the severity of psoriatic lesions and their response to therapy. In the PASI system, the body is divided into 4 regions: the head, trunk, upper extremities, and lower extremities. Each of these areas is assessed separately for the percentage of the area involved, which translates to a numeric score that ranges from 0 (indicates no involvement) to 6 (90%-100% involvement), and for erythema, induration, and scaling, which are each rated on a scale of 0 to 4. The PASI produces a numeric score that can range from 0 (no psoriasis) to 72. A higher score indicates more severe disease.

Efficacy endpoints related to the PASI score are defined below:

PASI 50 Responder

Subjects with $\geq 50\%$ improvement in PASI from baseline will be considered PASI 50 responders.

PASI 75 Responder

Subjects with $\geq 75\%$ improvement in PASI from baseline will be considered PASI 75 responders.

PASI 90 Responder

Subjects with $\geq 90\%$ improvement in PASI from baseline will be considered PASI 90 responders.

PASI 100 Responder

Subjects with 100% improvement in PASI from baseline (PASI score=0) will be considered PASI 100 responders.

Loss of PASI 90 Response

Defined as $< 90\%$ improvement in PASI from baseline after Week 16 in a participant who had achieved $\geq 90\%$ improvement in PASI from baseline at Week 16.

Loss of 50% of PASI Improvement

Defined as a loss of $\geq 50\%$ of the improvement in PASI at Week 16 after treatment is withdrawn.

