 - After retreatment with guselkumab: To evaluate the efficacy of retreatment with guselkumab, efficacy data at and after retreatment (ie, at the time of retreatment, 4 weeks after retreatment, 8 weeks after retreatment) will be summarized for subjects who were randomized to guselkumab at Week 0, were withdrawn from study agent

- at Week 16, experienced a loss of 50% of the Week 16 PASI improvement, and were retreated with guselkumab.
- For subjects who were randomized to placebo at Week 0, and were PASI 90 responders at Week 16, efficacy data will be listed after Week 16.
 - Efficacy of PASI 90 non-responders at Week 16
 - Efficacy analyses for those subjects who were PASI 90 non-responders at Week 16 will be performed for the following treatment groups.
 - ◆ **Placebo → Guselkumab:** Subjects who were randomized to placebo at Week 0, were PASI 90 non-responders at Week 16 and crossed over to guselkumab at Week 16.
 - ◆ **Guselkumab:** Subjects who were randomized to guselkumab at Week 0, were PASI 90 non-responders at Week 16 and continued to receive guselkumab at Week 16.
 - Efficacy of etanercept cross over subjects
 - ◆ **Etanercept → Guselkumab:** To evaluate the efficacy of guselkumab in subjects previously treated with etanercept, efficacy analyses will be performed from Week 20 through Week 52 for subjects who were randomized to etanercept at Week 0, and crossed over to guselkumab at Week 20.

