- The time to loss of 50% of the Week 16 PASI improvement (ie, time to retreatment) after withdrawal will be summarized for participants randomized to guselkumab group. The percent of subjects who experienced loss of 50% of Week 16 PASI improvement from Week 20 through Week 52 will be estimated from life-table methodology and cumulative incidence of loss of 50% of Week 16 PASI improvement curve will be presented.
- The time to loss of 50% of Week 16 PASI improvement will be summarized using life-table methodology for participants randomized to the guselkumab group who were PASI 90 responders at Week 16. The estimated number of weeks at which 90%, 75%, 50% and 25% of subjects experienced loss of 50% of Week 16 PASI improvement will be provided.
- The proportion of PASI responses (PASI 50, 75, 90, and 100) will be summarized over time through Week 52 for subjects randomized to the guselkumab group who were PASI 90 responders at Week 16. Non-responder status will be assigned after retreatment of guselkumab.
- The percent improvement from baseline in PASI will be summarized over time through Week 52 for subjects randomized to the guselkumab group who were PASI 90 responders at Week 16. PASI score at the time of retreatment will be carried forward after retreatment of guselkumab through Week 52.

PASI 90 responders at Week 16 (after retreatment of guselkumab)

- PASI score and PASI percent improvement at the time of retreatment with guselkumab will be summarized for subjects randomized to the guselkumab group who experienced loss of 50% of Week 16 PASI improvement.
- The PASI responses (PASI 50, 75, 90 and 100) with respect to baseline will be summarized over time (eg, 4 weeks after retreatment, 8 weeks after retreatment, 12 weeks after retreatment) following retreatment with guselkumab.

PASI 90 non-responders at Week 16

- The proportion of PASI responses (PASI 50, 75, 90, and 100) will be summarized over time through Week 52 by treatment group.

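### The extension summary after retreatment combines participants who relapsed with participants restarted at Week 52 without relapse, so its Week 60 and Week 84 rates do not estimate recapture of lost response

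*SAP*

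**What the plan says.** SAP 5.5.2.3 (Efficacy Analyses for Long Term Extension) ends with an additional summary of PASI responses, IGA responses, percent improvement in PASI and change in BSA. These "will be summarized at Week 60 and Week 84 after retreatment among guselkumab subjects who were withdrawn from guselkumab at Week 16". The participants included are those "retreated upon loss of response or at Week 52 if a loss of response was not observed at or prior to Week 52". Both restart routes sit in one population, and neither document orders a split by reason for restart.

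The second route is a real one. The long-term extension part of Protocol 6.1 provides: "Participants withdrawn from treatment at Week 16 who have not been retreated with guselkumab prior to Week 52 will receive a weight-based guselkumab dose". That dose falls at the Week 52 visit, with 8-weekly dosing afterwards.

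Elsewhere the SAP ties retreatment to relapse. Loss of response in SAP 5.1.2.2 is a loss of at least 50% "of the improvement in PASI at Week 16 after treatment is withdrawn". SAP 5.5.2.1 sets the main-study retreatment analysis on participants who "experienced a loss of 50% of the Week 16 PASI improvement, and were retreated with guselkumab". SAP 5.5.2.1.2.2 describes PASI at restart for "subjects randomized to the guselkumab group who experienced loss of 50% of Week 16 PASI improvement". SAP 7.1 limits the safety review after retreatment to those retreated on loss of response. Protocol 2.1 puts the question as "the ability to recapture response with retreatment following withdrawal from guselkumab".

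**The concern.** Recapture can be observed only in someone who has lost the response. A participant who restarts at Week 52 while still clear or nearly clear has nothing to recapture, yet counts as a responder in a table labelled as following retreatment. The combined rate then depends partly on how many participants never relapsed, which is not a property of retreatment.

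Efficacy of retreatment is a named secondary objective, and this is the only retreatment-specific efficacy summary planned for the period after Week 52. A reader of the study report could take its rates as evidence that lost response is regained, when part of the figure may be response that was never lost.

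**Working it through.** **1. Plan's own figure.** The documents give no expected rate for this summary, no relapse proportion and no retreatment response rate, so there is nothing to reproduce.

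**2. Disease state at restart.** Everyone withdrawn from guselkumab at Week 16 is a PASI 90 responder, so the Week 16 improvement I lies between 90% and 100% (SAP 5.1.2.2).

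- Relapser: has lost at least half of I, so remaining improvement is at most 0.5 × I, that is 0.5 × 90% = 45% to 0.5 × 100% = 50%. All are below PASI 75 at restart.
- No loss observed: remaining improvement at the last assessment is more than 0.5 × I, that is above 45% to 50%, with no upper limit short of 100%. Some may still be at PASI 75, 90 or 100; others may not.

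A later PASI 75, 90 or 100 response is therefore recapture in the first group by definition, and may be persistence in the second.

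**3. Populations compared.**

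| Analysis | Loss of response required? |
|---|---|
| SAP 5.5.2.1, main-study efficacy after retreatment | Yes |
| SAP 5.5.2.1.2.2, PASI at time of retreatment | Yes |
| SAP 7.1, safety after retreatment | Yes |
| SAP 5.5.2.3, extension Weeks 60 and 84 | No |

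**4. Effect on the rate.** Let f be the share of the summarised participants who relapsed, r their response rate and m the rate in those restarted without loss.

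Pooled rate = f × r + (1 − f) × m. Difference from the relapser rate = (1 − f) × (m − r).

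All values below are assumptions:

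| f | r | m | Pooled | Difference (points) |
|---|---|---|---|---|
| 0.25 | 60% | 90% | 82.5% | +22.5 |
| 0.25 | 80% | 90% | 87.5% | +7.5 |
| 0.50 | 60% | 90% | 75.0% | +15.0 |
| 0.50 | 80% | 90% | 85.0% | +5.0 |
| 0.75 | 60% | 90% | 67.5% | +7.5 |
| 0.75 | 80% | 90% | 82.5% | +2.5 |
| 0.50 | 90% | 80% | 85.0% | −5.0 |

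The difference is zero when m = r and takes the sign of m − r.

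**5. Re-exposure.** I read Weeks 60 and 84 as study weeks, because the extension schedule has Week 60 and then 24-weekly efficacy visits (60 + 24 = 84). Assessments precede dosing. At Week 60 a participant restarted at Week 52 has had one dose, 60 − 52 = 8 weeks earlier. A relapser retreated between Weeks 20 and 48 is 60 − 48 = 12 to 60 − 20 = 40 weeks past restart, with at least two doses. The groups thus differ in treatment received as well as in starting state.

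**6. Likely numbers.** About 30 + 10 = 40 participants are randomized to guselkumab in Part 1 (SAP 1.4). If the adult Week 16 PASI 90 rates in Protocol 2.2.1 applied (an assumption), 40 × 70.0% = 28.0 to 40 × 73.3% = 29.3 would be withdrawn, before any who do not enter the extension. With 28 in the table, one participant is 1/28 = 3.6 percentage points.

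**The case against.** The strongest reply is that the SAP never calls this summary a recapture estimate. It is an extra description of the extension on observed data, with no hypothesis test, and it states its composition openly. Recapture is addressed in the main study, in relapsers only, with IGA, PASI and BSA followed after retreatment; the 4, 8 and 12 weeks named there are examples rather than a limit. SAP 2.4.1.1 also lists a subset of withdrawn responders later retreated, with no loss-of-response condition, so the wider use of the word is not unique to SAP 5.5.2.3. All of this stands, and it keeps the point small.

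A reader might go further and infer that the pooled rate overstates recapture, because participants without loss count as responders whatever retreatment does. The documents do not support that. Keeping more than half of a 90% to 100% improvement guarantees only about 45% to 50%. It does not guarantee PASI 50 for everyone, and it guarantees nothing for PASI 75, 90 or 100. The SAP itself analyses loss of PASI 90 separately from loss of half the improvement. The lighter re-exposure of the Week 52 restarters at Week 60 could also lower their PASI 90 and 100 rates relative to relapsers.

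The reply does not remove the mixing. Uncertainty about the direction is itself a reason to separate the groups, since the single figure cannot be read either way.

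**Conclusion.** The point holds as one of interpretation, and it is minor. Followed as written, SAP 5.5.2.3 gives Week 60 and Week 84 rates that mix regained response with response that may never have been lost, in a population that departs from the SAP's relapser-only retreatment analyses. This rests on the definitions alone and needs no assumed rate.

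Overstatement is conditional: it occurs if participants without loss respond at a higher rate than relapsers. That is plausible from their better disease state at restart, but no figure in the documents shows it. The range of +22.5 to −5 points follows entirely from the chosen f, r and m and is illustrative. The co-primary and major secondary analyses, the Type I error and the main-study recapture analyses are not affected.

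**What to change.** In SAP 5.5.2.3, report Weeks 60 and 84 in two rows: (a) participants retreated because they met loss of response, including any whose loss is first seen at Week 52; and (b) participants restarted at Week 52 without loss of response. Give n and time since restart for each row, and use only row (a) to describe recapture after retreatment. State explicitly that Weeks 60 and 84 are study weeks, if that is what is meant.

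This takes a sentence or two of SAP text and one extra row. It needs no new data and does not touch trial conduct or error control. The cost is precision: each row is smaller than the pooled group, which may itself be fewer than 30 participants, so counts should be shown beside percentages.

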5.5.3. Data Handling

For the efficacy analyses in Part 1, data handling rules specified in Section 5.1.3 will be applied to all IGA, PASI, CDLQI, FDLQI, and BSA related analyses.

[figure not shown]
For the efficacy analyses in Part 2, data handling rules specified in Section 5.1.3 except rescue treatment rules will be applied to all efficacy analyses.

For the efficacy analyses in LTE, the data will be summarized based on observed.

6. USABILITY ASSESSMENTS

In Part 2 of the main study, pediatric participants ≥ 12 years of age and caregivers of pediatric participants of any age will be given the option to administer study agent. The usability of the CCI will be assessed for subjects with weight < 70 kg enrolled and treated in Part 2.

6.1. Definition

CCI

CCI

6.2. Analysis Methods

The following analyses for usability will be performed for all subjects enrolled and treated in Part 2 based on observed data without missing data imputation or other data handling rules.

- The Observer Injection Checklist will be summarized. A listing of Observer Injection Checklist results at Week 0 will be provided for subjects who did not correctly administer the injections.
- The CCI [REDACTED] and responses will be listed.
- A listing of product quality complaints (PQCs) associated with CCI [REDACTED] device will be provided for the safety analysis set in Part 1 and Part 2.

7. SAFETY

Safety will be assessed by summarizing the incidence and type of AEs and examining changes in laboratory parameters (hematology and chemistry), vital signs, and suicidal ideation and behavior.

In the safety analyses for Part 1, subjects who were randomized and received at least 1 (partial or complete) dose of study agent administration will be included and analyzed according to the treatment they actually received, regardless of the treatment assigned at randomization. No formal statistical comparison is planned.

For Part 2, the safety analyses will be performed for all subjects enrolled in Part 2 and treated.

For LTE, the safety analyses will be performed for all subjects entered in LTE and treated at or after Week 52.

Depending on the safety data categories, the cumulative safety data will be analyzed through different study periods which include but are not limited to through Week 16, through Week 52, and through the LTE as appropriate. Unless otherwise specified, tabular summaries of safety events for key study periods are in general presented as follows:

Summaries through Week 16 (placebo-controlled period in Part 1):

Safety data through Week 16 will be summarized by treatment groups:

- Placebo
- Guselkumab
- Etanercept

This allows between-group comparisons of safety between the guselkumab group, etanercept group and the placebo group based on similar follow-up period in each group.

Summaries through Week 52 in Part 1

Safety data through Week 52 will be summarized by treatment group defined as follows:

1. **Placebo → Guselkumab:** all subjects who were randomized to placebo at Week 0, started treatment with placebo only, and later crossed over to receive treatment with guselkumab. Only the safety events/measurements from these subjects that occurred on or after their first administration of guselkumab will be included in this group.

2. **Guselkumab:** all subjects who were randomized to guselkumab at Week 0 and were treated with guselkumab. All the safety events/measurements from these subjects that occurred beginning at Week 0 will be included in this group.
3. **Etanercept → Guselkumab:** all subjects who were randomized to etanercept at Week 0, started treatment with etanercept only, and later crossed over to receive treatment with guselkumab. Only the safety events/measurements from these subjects that occurred on or after their first administration of guselkumab will be included in this group.
4. **Combined Guselkumab:** all subjects as described above in the Placebo → Guselkumab, the Etanercept → Guselkumab and the Guselkumab groups.

In addition, the summaries of selected AE rates per hundred subject-years of follow-up through Week 52 will be provided.

Selected safety analyses will also be performed after retreatment with guselkumab among subjects who were randomized to guselkumab at Week 0, were PASI 90 responders at Week 16, were withdrawn from and then retreated with guselkumab.

Summaries through Week 52 in Part 2

Safety data through Week 52 will be summarized for all subjects who were enrolled in Part 2 and received at least 1 study agent administration of guselkumab. All the safety events/measurements from these subjects that occurred beginning at Week 0 will be included in this group.

Summaries through the LTE

Safety data through the LTE will be summarized for all subjects who participated in the LTE and were treated with guselkumab. All the safety events/measurements from Week 52 through the end of the study will be included in this group.

